## 5 Protocol Deviations

Any entered patient meeting one or more of the following criteria will be defined as major protocol violator:

- Participation in an interventional clinical study in which any treatment or follow-up is mandated
- Treatment with a GnRH receptor antagonist other than Firmagon
- Had previous or is currently under hormonal management of PCa, except for patients who have undergone therapy with a curative intention where neoadjuvant/adjuvant therapy allowed for maximum of 6 months. Treatment should be terminated at least 6 months prior to baseline.

These definitions yield at patient level (as opposed to patient and visit level). However, as no analyses are planned for the per-protocol population, there will be no practical implication of these definitions.

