## 1 Introduction

This study is a multi-centre, long-term, prospective, observational cohort study to be conducted in multiple countries in Europe. It constitutes a post-authorization safety study (PASS), to be conducted in compliance with Volume 9a of The Rules Governing Medicinal Products in the European Union (Guidelines on Pharmacovigilance of Medical Products for Human Use). Prostate cancer patients will enter the study after they begin treatment with androgen ablation therapy and will be followed for up to 5 years. Follow-up information will be collected every 3 months for the first 2 years and then every six months for the remaining 3 years or until patient discontinuation. There are no prescheduled visit regimens associated with the study. The visits in general should be part of routine clinical care and the information included into the study should also be part of the routine medical assessment. No procedures or examinations (e.g., physical exam, DEXA bone scan) are required as part of the study. Baseline data will be collected at a routine outpatient visit, follow-up data will be collected at the time of routine office visits or by telephone interviews at the approximate 3-month and 6-month time points.

All reasonable efforts and methods to minimize loss to follow-up will be undertaken to retain patients for the entire 5 years of observation, or until early discontinuation. This Observational study will enrol 1,000 patients treated with Firmagon. In addition, a comparator group of 500 patients treated with any GnRH agonist will also be enrolled. The primary aim of the study is to better understand the safety profile of Firmagon; however, inclusion of a comparator arm will provide the ability to understand the results in the more general context of androgen ablation and underlying PCa. Study enrolment will be monitored and enrolment of the control group will be locked once the target number of patients has been enrolled.

This document describes in details the planned statistical analyses for the FE200486 CS39 study protocol. The original protocol was dated on 25 Nov 2009.

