#### 3.1 Schedule of Assessments

Patients will be enrolled after the initial decision (by the investigator) has been made to introduce Firmagon or GnRH agonist as per label indication for prostate cancer. Data will be collected at baseline and every 3 months ( $\pm$  4 weeks) for the first 2 years, then every 6 months ( $\pm$  6 weeks) for the remaining 3 years. Firmagon is dosed monthly, while GnRH agonists may be administered less frequently, therefore suggested data collection time points *may not always* coincide with treatment-related clinical visits. If necessary, telephone outreach may be used by sites to collect relevant data. Patients who discontinue ADT therapy will continue to be followed for safety outcomes in order to assess the long term safety associated with ADT.

A flowchart of *recommended* study assessments is provided in [Table 1](#).

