#### **4 Patient Disposition**

All patients screened will be accounted for. All post-treatment allocation discontinuations (withdrawals) will be summarised by duration of study participation and main reason for discontinuation. All major protocol violations and withdrawals from trial will be summarised with frequency and percentage for each category of protocol violation or study discontinuation. The number of patients that were screened, already undergoing treatment when enrolled into the study, completed the trial, withdrew from trial will be summarised. Furthermore, the disposition/attendance of patients by visit-intervals will be provided. The number of patients screened but not allocated to treatment will be presented with the reason(s) for screen failure in a data listing.

In addition, the disposition of patients will be summarised with frequency and percentages after each follow-up visit (3 months interval for first 2 years and 6 months interval remaining 3 years).

Discontinuation rates will be estimated using the Kaplan-Meier (KM) method on time to discontinuation from date of enrolment, and graphically represented in corresponding 1-KM curves, differentiated for reason of discontinuation via cumulative incidence functions. Differences in discontinuation rates will be tested using the Log Rank test ( $\alpha=0.05$ , two-sided).

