**Table 4: Exposure periods for a patient dosed prior to signing the informed consent**

Event	First Dose of ADT	Signature of IC	Changing treatment regimen
Exposure Period	Pre-consent Period	Main Treatment Period	Post Main Treatment Period

It could also be that the patient signs the informed consent before being dosed. This scenario would lead to the definition of a “Pre-exposure Period”. However, an adverse event occurring before first dose is defined as non-treatment emergent and will not be reported.

Considering AESIs occurring during the “Main Treatment Period” can strengthen the validity of the comparison of the treatment effects on these AEs.

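### The third major-violation criterion does not exempt the index ADT, and patients with non-permitted earlier hormonal therapy stay in every comparison without a sensitivity analysis

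*SAP*

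**What the plan says.** SAP Section 5 (Protocol Deviations) gives three criteria, any one of which makes an entered patient a major violator. The third reads: "Had previous or is currently under hormonal management of PCa, except for patients who have undergone therapy with a curative intention". The exception covers neoadjuvant or adjuvant therapy of at most 6 months and adds: "Treatment should be terminated at least 6 months prior to baseline". Section 5 closes by saying that "as no analyses are planned for the per-protocol population, there will be no practical implication of these definitions".

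Other sections describe who enters and how they are handled:
- Section 1: "Prostate cancer patients will enter the study after they begin treatment with androgen ablation therapy".
- Section 3.1 words entry differently: "Patients will be enrolled after the initial decision (by the investigator) has been made to introduce Firmagon or GnRH agonist". This does not require a first dose.
- Section 4 plans a disposition count of patients "already undergoing treatment when enrolled into the study". It also states: "All major protocol violations and withdrawals from trial will be summarised with frequency and percentage", by category.
- Section 7 sets baseline information to missing for Firmagon patients who are already on the drug at the baseline visit.
- Section 8.1 defines a pre-consent period, and Table 4 places "First Dose of ADT" ahead of the consent signature.

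Sections 6 and 6.1 put all analyses on dosed patients by treatment received.

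**The concern.** There are two linked problems.

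First, the criterion speaks of any current hormonal management without setting aside the drug under study. A patient who enters in the way Section 1 describes meets it. The violation table would then place patients enrolled as intended in the same category as patients whose earlier hormonal therapy was not permitted, and the reader could not tell from that count how many of the second kind there are.

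Second, the patients whom the criterion is presumably meant to catch remain in the Poisson, Kaplan-Meier and Cox comparisons, and nothing in the plan shows whether they matter. An example is a man moved from an agonist to Firmagon before entry. This fits poorly with Sections 8.1 and 10.4.1, which confine AESIs to the main treatment period in order to reduce bias from overlapping treatments. A change of ADT after entry ends that period, but a change before entry has no consequence. At stake are the Firmagon event rates (the primary objective) and the comparison with the agonists (a secondary objective).

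**Working it through.** The point rests on wording, so the sections are compared first. The arithmetic afterwards is illustrative.

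**Comparison of the text**
1. Does the exception in Section 5 cover a patient on the index ADT at entry? No. It requires curative intent, and the therapy must have ended at least 6 months before baseline. Treatment that is still running cannot satisfy that.
2. Does the plan expect such patients? Yes: in Section 1 (entry), Section 4 (disposition), Section 7 (baseline rule, for Firmagon) and Section 8.1 with Table 4 (pre-consent period).
3. Are all patients affected? Not necessarily. Section 3.1 allows entry once the decision to treat is made, and Section 8.1 also provides for consent before the first dose.
4. Are true violators removed or adjusted for anywhere? The Safety Analysis Set excludes none. The Section 10.5.1 models adjust for age, stage and, except for mortality, one relevant history item; Section 10.5.3 uses the same factors. Sections 10.6.4 and 10.6.6 name age, stage and prior CVD as a minimum. No term for earlier hormonal therapy is named and no sensitivity analysis is described.

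**When would the IRR be biased?** Let fF and fG be the shares of patients with non-permitted earlier therapy in the Firmagon and agonist arms, and r their event rate relative to the other patients in the same arm. With a true IRR of 1,

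observed IRR = [1 + fF(r − 1)] / [1 + fG(r − 1)].

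The SAP gives none of these three values. All of the following are assumptions:

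| fF | fG | r = 1.25 | r = 1.5 | r = 2 |
|---|---|---|---|---|
| 10% | 10% | 1.00 | 1.00 | 1.00 |
| 5% | 15% | 0.98 | 0.95 | 0.91 |
| 5% | 25% | 0.95 | 0.91 | 0.84 |
| 15% | 5% | 1.02 | 1.05 | 1.10 |
| 25% | 5% | 1.05 | 1.10 | 1.19 |

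Equal shares with the same r leave the IRR unchanged. Unequal shares can move it either way.

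**What would a sensitivity run cost in precision?** Section 3.2 assumes 10% dropout spread uniformly over 5 years:
- Firmagon: 900 × 5 + 100 × 2.5 = 4,750 patient-years.
- Agonist: 450 × 5 + 50 × 2.5 = 2,375 patient-years.

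As a check against Table 2, 5 per 100 patient-years over 4,750 gives 237.5 events. With 238 events the exact Poisson interval is 4.39–5.69. The table has 4.38–5.68, with the same width of 1.30.

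Assume 5 cardiovascular events per 100 patient-years in both arms, and CI = exp(±1.96 × √(1/EF + 1/EG)) around an IRR of 1, where EF and EG are the expected events:
- No exclusion: EF = 237.5, EG = 118.75, SE = 0.112, CI 0.80–1.25.
- 10% excluded: EF = 213.75, EG = 106.875, SE = 0.118, CI 0.79–1.26.
- 20% excluded: EF = 190, EG = 95, SE = 0.126, CI 0.78–1.28.

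**The case against.** The criterion reads like an eligibility rule: it speaks of permitted earlier therapy, a maximum duration and a gap before baseline. Its natural target is hormonal therapy other than the study drug, and the rest of the SAP treats patients already on the index drug as ordinary. The protocol, which may word this better, is not at hand. That is a fair account of what the authors probably meant. It does not change what Section 5 says, and the Section 4 table will be programmed from Section 5.

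Keeping all dosed patients is normal for a safety study with a descriptive primary objective, and Section 6.1 takes that set from the protocol. This stands in full. Retention is not the fault, and the closing sentence of Section 5 is accurate about the planned analyses. What is missing is any way to see the effect of these patients.

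The SAP also separates more than it might seem. Treatment with another GnRH antagonist is a criterion of its own, so those patients are not hidden in the mixed category. Section 4 counts patients already on treatment separately, and Section 7.3 summarises previous therapies and lists their dates. These outputs would help a reader to reconstruct the split but do not provide it.

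A reader might infer that the violation count will consist mainly of patients enrolled as intended. No section gives a count, and Section 3.1 allows entry before dosing, so this cannot be asserted.

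**Conclusion.** The point holds as an inconsistency of wording that reaches one planned table, together with a missing sensitivity analysis for patients with non-permitted earlier hormonal therapy. Sections 1, 3.1, 4, 5 and 8.1 need to be reconciled.

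The direction and size of any bias are unknown. The assumed shares and rate ratios in the table move a true IRR of 1 to between 0.84 and 1.19. They show only that an effect is possible when the arms differ, not that one is expected.

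Two stronger readings are tempting. One is to mix the CS21 fracture rates in Section 3.2 (0.6 and 2.2 per 100 patient-years) and report a large inflation of the Firmagon rate. That would need a share of switched patients that the SAP does not give, contamination in one arm only, and full persistence of the agonist rate after the switch. It would also describe the wrong endpoint, since the AESI analysed as bone fracture is defined by serious events in the osteonecrosis SMQ (Section 10.4.1). The other is to say that all AESIs build up with cumulative androgen deprivation. Section 3.2 links risk to the number of agonist doses for fractures only.

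**What to change.** 1. Reword the third criterion as hormonal management of PCa other than the index ADT, define the index ADT as the Firmagon or agonist under which the patient is enrolled, and leave the eligibility limits as they are. Bring Sections 1, 3.1, 4 and 8.1 into line with it and check it against the protocol.
2. Tabulate the violators that remain by arm and category, and show the prior drug class where it was recorded. Section 7.3 promises the type and dates of earlier therapy but does not show that drug class was captured.
3. Replace the closing sentence of Section 5 with one pre-specified sensitivity analysis: rerun the Section 10.5.1 Poisson and Section 10.5.3 Cox models without these patients. The primary analysis stays on all dosed patients.

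The cost is a wording change, one table split and one further run of models that already exist. The downside is somewhat fewer patient-years in the sensitivity run, with the small loss of precision shown above.

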## **6 Analysis Dataset**

As the study is non-randomised the intention to treat principle (analyses according to the planned treatment regimen) will not be followed. All analyses will be performed on the actual (received) treatment.

### **6.1 Safety Analysis Set**

The protocol states that “The statistical analyses will be performed on the safety analysis set, which comprises all patients treated with at least one dose of medicinal product.” Patients who never enter the main treatment period (being dosed and having signed the informed consent (see Section 8) will not be included in the Safety Analysis Set.

## 7 Study Population

All tabulations and listings will be based on the safety analysis set.

Categorical data will be summarised using numbers and percentages. The percentages are based on the total number of patients with a corresponding assessment relative to the total number of patients in the safety analysis set. Continuous data will be presented using the number of patients (N), mean and standard deviation, median, minimum and maximum. All baseline characteristics will be listed.

In case of study patients enrolled to the Firmagon group are already on the treatment at the time of the baseline visit and baseline data registration, the baseline information will be defined missing as their baseline data may already be affected by the treatment.

Missing values will not be imputed. If the timing of the dose of a concomitant medication cannot be established in relation to the administration of study drug, it will be considered as a treatment emergent concomitant medication (see Section 7.7).

### 7.1 Demographics

Demographic variables (e.g., age, race and ethnic origin, height, weight and BMI) will be summarised by treatment group.

### 7.2 Vital Signs at Baseline

Vital signs, as far as collected at baseline, will be summarised by treatment group.

### 7.3 History and Stage of Prostate Cancer

A summary table of history and stage of PCa will be presented, containing the following information:

- number of patients diagnosed with PCa
- previous cancer therapies (Radical Prostatectomy, Radiotherapy Neoadjuvant/Adjuvant Hormonal Therapy, and Other)
- ECOG (Eastern Cooperative Oncology Group) performance status, a score in the range of 0 (=fully active) to 4 (=completely disabled)
- Pathological stages of primary tumor (pT) and regional lymph node (pN) (for patients having undergone radical prostatectomy only) (as defined below)
- Gleason score (as defined below)
- stage of prostate cancer (TNM classifications) (as defined below)
- PSA baseline category (as defined below)

The following pathological stages will be recorded and summarized by treatment group:

pT (primary tumor)

- Not done
- Not applicable
- PT2
- PT3MR-
- PT3MR+

pN (regional lymph node)

- Not done
- Not applicable
- PN0
- PN1
- PN2/3

The Gleason score is calculated as the sum of the Gleason grade of the primary and secondary patterns. The following categories will be presented:

- 2-4
- 5-6
- 7-10

The stage of prostate cancer, based on the TNM classification, includes the following categories:

- Localised: T1/2 & (NX or N0) & M0,
- Locally Advanced: [T3/4 & (NX or N0) & M0], or [N1 & M0],
- Metastatic: M1
- Not classifiable: Results from T, N, and M categories that could not be resolved to Localised, Locally Advanced, or Metastatic

The following baseline PSA categories will be used:

- [0-10] ng/mL
- ]10-20] ng/mL
- ]20-50] ng/mL
- ]50- ] ng/mL

Dates of diagnosis, and start (and stop) of previous therapies will be presented in patient listings.

#### 7.4 Baseline Risk Factors: Substance Use

The following baseline risk factors for cardiovascular disease and bone fractures / osteoporosis / osteopenia will be summarized (in one table) by treatment group. Frequency of the following activities (amounts will be presented in data listings)

- smoking (categories: Not done / Never / Former / Current)
- alcohol consumption (categories: Not done / Never / Former / Current)
- level of physical activity (categories: Not done / Rare or Never / Monthly / Weekly)

#### 7.5 Dual Energy X-ray Absorptiometry (DEXA) Bone Scan, as Available

Baseline results of bone mass density (BMD) on proximal femur and total lumbar spine, will be summarized by treatment group.

The T-Score compares the bone density to that of young healthy adults in units of standard deviations (SD) [7]. The severity of osteoporosis will be classified based on Table 3. If no T-score is obtained, the severity of osteoporosis is “non-classified”. The number of patients (and percentage) in each category will be tabulated by treatment group.

**Table 3: World Health Organization Definitions Based on Bone Density Level [7]**

Severity of Osteoporosis	Range in T-Score
Non-Classified	No T-score present
Normal	Bone density is within 1 SD (+1 or -1) of the young adult mean.
Low bone mass	Bone density is between 1 and 2.5 SD below the young adult mean (-1 to -2.5 SD).
Osteoporosis	Bone density is 2.5 SD or more below the young adult mean (-2.5 SD or lower).
Severe (established) osteoporosis	Bone density is more than 2.5 SD below the young adult mean, and there have been one or more osteoporotic fractures.

#### 7.6 Medical History

##### 7.6.1 Medical History by MedDRA SMQ Terminology

Medical history recorded at screening visit will be coded using MedDRA and summarised by Primary System Organ Class (SOC) (alphabetically), and Preferred Term (PT) in decreasing order of frequency by treatment.

The following tables will also be presented for the AE in medical history of special interest; i.e. events within the broad scope of the SMQ codes in Appendix 4:

- Medical history of cardiovascular events
- Medical history of diabetes mellitus
- Medical history of fractures
- Medical history of cardiovascular events (explorative analysis)

These tables will be sorted by MedDRA SMQ term (in decreasing frequency of occurrence) and PT (in decreasing frequency of occurrence).

Furthermore, medical history will be presented in patient data listings.

#### **7.6.1.1 Medical History of Events During Pre-consent Period**

For the events (defined as in Section 7.6.1) that occur during the pre-consent period, see Section 8, a listing will be prepared with the following contents: subject number; treatment; start date, end date of coded SMQ term; first exposure date; first visit date and date of signed informed consent.

#### **7.6.2 Medical History as Recorded in the eCRF**

##### **7.6.2.1 Medical History of Special Interest**

Occurrence (yes/no) of medical history of the following risk factors is recorded in the eCRF:

- hyperlipidemia
- hypertension
- diabetes mellitus
- hepatic disorders
- renal disorders
- cardiovascular disease
- osteoporosis

Each category above will be presented by actual number and percentage of total in safety analysis set.

##### **7.6.2.2 Relevant Family History**

Occurrence (yes/no) of family history of the following risk factors is recorded in the eCRF:

- prostate cancer

- cardiovascular disease
- diabetes mellitus
- osteoporosis

Each category above will be presented by actual number and percentage of total in safety analysis set.

### **7.7 Concomitant Medication**

Prior and concomitant medication will be summarised by ATC classification 1st level (alphabetically), ATC classification 2nd level (in decreasing order of frequency) and treatment group. These medications will be summarized by treatment for:

- 1) Prior medication; i.e. medication taken exclusively prior to treatment (i.e. with stop date before date of first drug administration);
- 2) Concomitant medication, i.e. medication taken during the treatment period (i.e. medication that was not stopped before date of first drug administration and not started after the last drug administration).
- 3) Post-treatment medications, i.e. medications starting after the treatment period (i.e. with start after the last drug administration).

Furthermore, concomitant medication will be presented in patient data listings.

### **7.8 Physical Exam**

No specific procedures with respect to physical examination are planned as part of the trial. If any physical examination is carried out, and there are any abnormalities at patient level, this data will be listed.

### **7.9 Explorative Cardiovascular Disease (CVD) Population**

The explorative CVD population is defined as those patients with at least one event belonging to the broad scope of any of the following five SMQs: Myocardial infarction; Ischaemic cerebrovascular conditions; Haemorrhagic cerebrovascular conditions; Embolic and thrombotic events, arterial, Other ischaemic heart disease. (Details of SMQ codes are found in Appendix 4.)

One table, presenting the agreement between medical history of cardiovascular disease as reported by the patient (Section 7.6.2.1), and history of cardiovascular disease as identified by the SMQ (Section 7.6.1) will be presented for the overall population.

For the explorative CVD population the following tables will be presented as part of the explorative analysis:

- Demographics as in Section 7.1

- History and Stage of Prostate Cancer, as described in Section 7.3
- Medical History, Section 7.6.

